6.3.1 Part B Specific Inclusion criteria

Diagnosis of rheumatoid arthritis made by a Rheumatologist within the previous 2 years

6.4 Other study eligibility criteria considerations

In order to assess any potential impact on subject eligibility with regard to safety, the Investigator must refer to the relevant document(s) for detailed information regarding warnings, precautions, contraindications, adverse events, and other significant data pertaining to the study product being used in the study. Such documents may include, but not limited to the Clinical Investigator's Brochure (IB) or equivalent document provided by the Sponsor.

6.4.1 Contraception

All women of child bearing potential (defined as sexually mature women who have had menses within the preceding 24 months and have not undergone hysterectomy, bilateral oophorectomy or tubal ligation) must have a negative serum pregnancy test (with a sensitivity of at least 50 International Units/mL) performed at Screening and Baseline and prior to scheduled administration of investigational product.

Women of child bearing potential must agree not to attempt to become pregnant or undergo *in vitro* fertilisation and, if participating in sexual activity that could lead to pregnancy, must use two reliable methods of contraception simultaneously while receiving protocol-specified medication and for 28 days after stopping the medication. Male subjects must agree to use two reliable methods of contraception simultaneously while receiving protocol-specified medication and for 28 days after stopping the medication if their partner is of child bearing potential.

A combination of two of the following methods must be used:

- Condoms (male or female) with or without a spermicidal agent;
- Diaphragm or cervical cap with spermicide;
- Intra Uterine Device;
- Hormonal-based contraception.

Women who are not of child bearing potential are not required to use contraception.

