Committees / guidelines:	DEN-181 Safety Monitoring Committee
Special protocol requirement:	None

CONFIDENTIAL

Table 1-1 Table of Assessments

Assessment	Screening	On-Study Period				Exit Evaluation
	Day -35 to -1	D 1	D8	D15	D29	D57
	Visit 1	Visit 2	Visit 3	Visit 4	Visit 5	Visit 6
Written Informed Consent	X					
Eligibility Assessment/Confirmation	X	X				
Medical History	X					
Physical Examination (symptom directed)	X	X	(X)	(X)	(X)	(X)
Vitals Signs/Body Weight/Height ^{1,2,3,4}	X	X	X	X	X	X
Electrocardiogram	X					
Pregnancy Test ⁵ (Part B only)	X	X	(X)	(X)		X
HIV & Hepatitis Serology	X					
HLA Typing (if required)	X					
anti-CCP2	X				X	X
Rheumatoid Factor (RF)	X					
Issue Injection Site Reaction Diary (Part B only)		X	(X)	(X)		

CONFIDENTIAL

Assessment	Screening	On-Study Period				Exit Evaluation
	-35 to -1	D1	D8	D15	D29	D57
	Visit 1	Visit 2	Visit 3	Visit 4	Visit 5	Visit 6
Review Injection Site Reaction Diary (Part B only)			X	(X)	(X)	
Haematology including ESR	X	X	X	X	X	X
Chemistry including CRP	X	X	X	X	X	X
Urinalysis	X	X	X	X	X	X
DAS28CRPv4 evaluation	X	X	X	X	X	X
PBMC processing and storage		X	X		X	
Tetramer Analysis (collagen II and HA)		X	X		X	
Exploratory immune and biomarker assays		X	X		X	X
Plasma Calcitriol assay ⁶ (Part B only)		X	(X)	(X)		
Oral swab; microbiome analysis		X				X
Dispense IMP (Part B only)		X	(X)	(X)		
Administration of IMP (Part B only)		X	(X)	(X)		
Adverse Event		X	X	X	X	X
Concurrent Medications Assessment	X	X	X	X	X	X

CONFIDENTIAL

DEN-181

Dendright Pty Ltd

¹ Height and weight to be performed at Visit 1 only

² Vital signs include resting BP, heart rate, respiratory rate and oral temperature

³ Safety assessments to be performed prior to IMP

⁴ Vital signs to be performed prior to IMP administration and at 15 minutes and 30 minutes following dosing

⁵ Serum pregnancy testing will be conducted in female participants of childbearing potential at Screening. Urine pregnancy testing will be conducted before each administration of IMP. If urine pregnancy test is positive, a serum pregnancy test will be conducted and the IMP will not be administered until the result of this is received. If the result of the serum pregnancy test is negative, administration of IMP will continue. If the result of a serum pregnancy test is positive, the participant will be withdrawn from the study.

⁶ Blood collected for calcitriol assay pre-dose and at 1, 2 and 4 hours after IMP administration

CONFIDENTIAL

Protocol No. DEN-17-01-RA
Version 3.0

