6.2 Inclusion criteria

The criteria for entry into the study are:

1. Diagnosis of rheumatoid arthritis made by a rheumatologist;
2. HLA-DRB1*0401+, HLA-DRB1*0101+ or HLA-DRB1*0401+HLA-DRB1*0101+ heterozygotes, homozygotes or compound heterozygotes; and ACPA+ (anti-CCP2>6);
3. Treatment with MTX at the same dose for at least 2 weeks prior to planned start of trial treatment;
4. Any swollen joint count at screening (0-28);
5. Age 18-75 years (male or female) inclusive;
6. Patients must be informed of the investigational nature of this study and give voluntary written informed consent in accordance with the institutional and hospital guidelines;
7. Male or Female. Females of child-bearing potential must agree to use two effective forms of contraception from enrolment to completion of the study;
8. Blood glucose, CBC, haemoglobin, platelets, creatinine, bilirubin, and AST/ALT not greater than 1.5 times out of normal range at entry and clinically insignificant in the opinion of the investigator;
9. Patients agree to forego vaccinations during the course of the study;

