7.4.6 Pregnancy tests

Serum pregnancy testing will be conducted for female subjects of childbearing potential at screening (visit 1). Before administration of the IMP (visit 2), visit 3 (Part B only), visit 4 (Part B only) and at the end of the study (visit 6) a urine pregnancy test will be performed.

If the urine pregnancy test is positive at visit 2, visit 3 (Part B only) or visit 4 (Part B only) a serum pregnancy test will be conducted to confirm the urine-based test and the IMP will not be administered until a negative result is obtained. If the serum pregnancy test is positive, the patient will be excluded or withdrawn from the study.

If the result of the urine pregnancy test is positive at visit 6, a serum pregnancy test will be conducted to confirm the urine-based test. If the serum-based test is positive at any visit, procedures for reporting a Clinical Trial Pregnancy will be performed.

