10.9 Risks for women of childbearing potential or during pregnancy

The risks of treatment with Study Product during pregnancy have not been evaluated. Pre-menopausal women of childbearing potential will follow a medically prescribed birth control regimen or agree to abstain from heterosexual intercourse while participating in the study and for 30 days following the last dose of Study Product.

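### Section 6.4.1 defines childbearing potential by menses in the last 24 months whatever the reason for their absence, so read literally some fertile women, and male subjects with such partners, are released from its two-method contraception rule

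*Protocol*

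**What the plan says.** Protocol 6.4.1 gives the only definition of childbearing potential in the document: "defined as sexually mature women who have had menses within the preceding 24 months and have not undergone hysterectomy, bilateral oophorectomy or tubal ligation". Women who meet it must have negative serum pregnancy tests at screening, at baseline and before each scheduled dose, must agree not to try to conceive, and must use two methods at once during treatment and for 28 days afterwards. The section then states: "Women who are not of child bearing potential are not required to use contraception". Male subjects have the same two-method duty, during treatment and "for 28 days after stopping the medication if their partner is of child bearing potential".

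The term recurs elsewhere without a definition or a reference to 6.4.1:

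- Inclusion criterion 7 in 6.2 (criterion 6 in the synopsis): "Females of child-bearing potential must agree to use two effective forms of contraception from enrolment to completion of the study".
- Section 10.9: "Pre-menopausal women of childbearing potential will follow a medically prescribed birth control regimen or agree to abstain from heterosexual intercourse", while in the study and for 30 days after the last dose.
- Table 1-1, footnote 5: "Serum pregnancy testing will be conducted in female participants of childbearing potential at Screening". Section 7.4.6 limits the screening serum test in the same way.

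The synopsis, under study procedures, words both serum and urine testing for female participants generally, with no such limit.

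**The concern.** Recent menses is a necessary condition in the definition, and nothing qualifies it by menopause, age, hormone level or cause. Absence of menses for two years is a reasonable marker of menopause only when no other cause explains it. A woman with intact reproductive organs whose amenorrhoea is long-standing but reversible can still conceive, or can do so once the cause is removed, yet the definition places her with post-menopausal women. One possible cause is hormonal contraception, which 6.4.1 itself lists as an acceptable method.

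What is at stake is subject safety in a first-in-human trial. Section 10.9 says: "The risks of treatment with Study Product during pregnancy have not been evaluated". The sponsor judged two simultaneous methods necessary, and its own definition excuses some of the people that judgement was meant to cover. Contraception and eligibility rules belong in the protocol, so this is not something left for the statistical analysis plan.

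**Working it through.** The protocol gives no figure to reproduce. The check is a reading of the rule, followed by counts from the visit schedule.

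**1. Who falls outside the definition.** Two conditions are joined by "and": menses within 24 months, and none of three operations. Failing either one is enough to be outside. A woman with no relevant surgery and reversible amenorrhoea of more than 24 months fails the first condition. Women from age 18 are eligible (6.2), so women of reproductive age are in scope. Section 6.4.1 then expressly says that she need not use contraception.

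**2. What still binds her.** This depends on whether the 6.4.1 definition governs the other sections, and they do not say.

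| Reading of the term | Criterion 7 | Section 10.9 | Methods required |
|---|---|---|---|
| 6.4.1 definition governs everywhere | lapses | lapses | 0 |
| It governs criterion 7 but not 10.9 | lapses | binds | one regimen, or abstinence |
| Ordinary meaning in criterion 7 | binds | either | 2 |

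**3. How long each duty would have run.**

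- Section 6.4.1, last dose plus 28 days: Part A, Day 1 + 28 = Day 29; Part B, Day 15 + 28 = Day 43.
- Criterion 7, to study completion: Day 57.
- Section 10.9, during the study and to last dose plus 30 days: Day 31 in Part A and Day 45 in Part B. Both fall before Day 57, so participation to Day 57 sets the end.

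**4. Male subjects.** Criterion 7 and 10.9 address women only, so 6.4.1 is the single male rule. If the partner falls outside the definition, the requirement drops from 2 methods to 0 and no other section restores it. Partners are not tested. Section 10.10 requires a partner's pregnancy to be reported, which comes after the event.

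**5. Pregnancy tests.**

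| | Part A | Part B |
|---|---|---|
| Serum tests that 6.4.1 limits to the definition | screening, Day 1 (2) | screening, Days 1, 8, 15 (4) |
| Urine tests in 7.3.2 to 7.3.4, no stated limit | Days 1, 57 (2) | Days 1, 8, 15, 57 (4) |
| Testing occasions in all | screening, Days 1, 57 (3) | screening, Days 1, 8, 15, 57 (5) |
| Lapsed serum tests matched by a same-day urine test | 1 | 3 |
| Occasions lost | 2 − 1 = 1 of 3 | 4 − 3 = 1 of 5 |

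The occasion lost is screening. Under the synopsis wording, none is lost.

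**The case against.** **The other sections may still protect her.** Criterion 7 does not cite the 24-month test, and in ordinary usage a fertile woman on a hormonal method is of childbearing potential. Section 10.9 adds the word pre-menopausal, which would do little work if the 24-month test already governed. An investigator could therefore apply criterion 7 and require two methods to Day 57. This stands. A reader might infer that her requirement falls from two methods to none; the documents support only a range of 0 to 2. It does not remove the defect, because 6.4.1 gives the only definition and attaches an express exemption to it.

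**The likeliest case already uses contraception.** A woman whose amenorrhoea comes from a hormonal method has one accepted method in place, so the practical gap is one more. This also stands, although on the literal reading 6.4.1 does not oblige her to continue the first.

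**The urine tests may not be unlimited.** In 7.4.6 and footnote 5, the urine sentence follows one restricted to women of childbearing potential and could be read as sharing that limit. This is possible. No limit is stated, however, and the visit lists carry none. A reader might infer that testing as a whole falls away; the text does not support that.

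**Other material may close the gap.** Section 6.4 sends the investigator to the Investigator's Brochure, and the consent pages were not available. Neither can be assumed to correct a rule that the protocol states expressly.

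**The male-partner case is remote.** It needs a male subject and a fertile partner with more than 24 months of reversible amenorrhoea. That limits how often it arises, but the text leaves no second rule to fall back on when it does.

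**Conclusion.** The point holds as a minor safety correction. By its literal wording, 6.4.1 treats some women who can still conceive as not of childbearing potential and excuses them from two methods and from the agreement not to attempt pregnancy. It also excuses male subjects whose partners are in that position, and for them no other section applies.

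For a female subject the methods required range from 0 to 2, depending on how criterion 7 and 10.9 are read. For an affected male subject they are 0. The serum tests that 6.4.1 requires lapse (2 in Part A, 4 in Part B), but about one testing occasion is lost in practice, or none under the synopsis. That count assumes that the urine tests in the visit lists apply to all female subjects, as they appear to.

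The number affected among at most 58 subjects cannot be derived from the protocol and is probably small. A reader might infer a wider failure of pregnancy protection or an effect on the results. Neither follows: testing on dosing days appears to remain, pregnancies must be reported, and no endpoint, analysis set or estimate depends on this definition.

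**What to change.** Amend 6.4.1 so that 24 months without menses removes childbearing potential only when it is due to menopause, and not to contraception or another medical or reversible cause. Leave the surgical exemptions as they are. Cite that definition in inclusion criterion 7 (synopsis criterion 6), 7.4.6, Table 1-1 footnote 5 and 10.9, so that one meaning applies throughout. The exact clinical wording is for the sponsor's medical team.

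The cost is one clause and a few cross-references, submitted as a protocol modification. The burden on subjects is a second contraceptive method and the serum tests for the few women reclassified, and two methods for the few male subjects whose partners are reclassified.

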6.4.2 Renal Function

Renal function eligibility may be determined by either estimated creatinine clearance calculated by Cockcroft-Gault or serum creatinine, as clinically indicated.

The Cockcroft-Gault Formula to be used is:

$$\text{Creatinine clearance (mL/min)} = \frac{(140 - \text{age}) \times (\text{Bodyweight in kg}) \times (0.85 \text{ if female})}{(72 \times \text{Serum creatinine (mg/dL)})}$$

6.4.3 Rescreening

Subjects with laboratory abnormalities that are exclusionary, but inconsistent with previous history, may be re-tested twice (3 total tests) within a window of 56 days. Rescreening of these subjects must be discussed and agreed with the Sponsor or designee prior to enrolment in the study.

7 SCHEDULE OF ASSESSMENTS AND PROCEDURES

7.1 Study schedule of evaluations

The schedule of assessments is presented in Table 1.

7.2 Visit windows

Every effort should be made to keep to the study schedule.

Study Period	Acceptable Window
Screening	± 3 days
On-study (dosing)	± 2 days
Follow-up	± 7 days

The Sponsor or designee must approve all visits outside of these windows.

7.3 Study procedures / assessment period

The study procedures to be conducted for each subject enrolled in the study are listed below and in Section 7.4.

All laboratory tests on blood and urine samples will be performed at the designated local laboratory. Immunological assessments to support study objectives (non-exploratory endpoints) and measurements of calcitriol concentrations in plasma will be performed at central laboratories. Refer to the Study Reference Manual.

Additional visits and/or assessments may be conducted as clinically indicated.

7.3.1 Visit 1 Screening visit

Subjects will be screened within 35 days prior to randomisation to determine eligibility for participation in the study. The following will be performed and documented at Screening:

- Obtain written informed consent. (This must be completed prior to any other procedure)
- A screening medical history (see Section 7.4.1)
- A complete physical examination including: (see Section 7.4.1)
 - Vital signs
 - Bodyweight
 - Height
 - Assessment of all appropriate body systems to determine study eligibility
- Electrocardiogram (See section 7.4.2)
- Concurrent medication assessment (See Section 9)
- Blood samples for
 - Haematology including ESR (See section 7.4.3)
 - Clinical chemistry including CRP (See section 7.4.3)

- Viral serology for HIV, HBV and HCV (See section 7.4.3)
- Pregnancy testing (See Section 7.4.6)
- Blood samples for immunological assessments including:
 - HLA typing (if not already part of the participant's medical record; see Section 7.4.3)
 - Anti-CCP2 titre (See Section 7.4.3)
 - Rheumatoid Factor (See Section 7.4.3)
- Urine samples for urinalysis (see Section 7.4.2)
- DAS28CRPv4 evaluation (See section 7.4.7)

Subjects meeting the inclusion criteria and none of the exclusion criteria will return to the clinic within 35 days after screening for randomisation. If the patient misses randomisation and requires rescreening within a new 35 day window, blood samples for hematology and clinical chemistry including CRP, and pregnancy testing (if relevant) only are required to be repeated. The other laboratory and clinical data from the previous screen may be used, and updated with any relevant medical history/examination and medications.

7.3.2 Visit 2 (Day 1) baseline evaluations, randomisation, and study medication dispensing

At Visit 2 the following tests will be performed and documented on the Case Report Form (CRF) prior to administration of the IMP:

- Review of inclusion/exclusion criteria (see Section 6.2 and 6.3)
- Urine samples for urinalysis and pregnancy testing (see Section 7.4.3 and 7.4.6)
- A complete physical examination (see Section 7.4.1)
- Vital signs (see Section 7.4.1)
- Concurrent medication assessment (see Section 9)
- Adverse event questioning (see Section 10)
- DAS28CRPv4 evaluation (see section 7.4.7)
- Blood samples for:
 - Haematology including ESR (see Section 7.4.3)
 - Clinical chemistry including CRP (see Section 7.4.3)
- Blood samples for immunological assessments including (See sections 7.4.3 and 7.4.4):
 - Tetramer analysis (Collagen II and HA)
 - Exploratory Immune assays
- Blood samples for calcitriol concentration assessment (See Section 7.4.3)
- An oral swab will be (See Section 7.4.8)

Once the above assessments have been performed the patient will be randomised and the IMP will be administered.

- Subjects will be observed and vital signs will be measured at 15 and 30 minutes following the administration of IMP
- Subjects will remain in the clinic for at least four hours post-administration of IMP
- Blood samples for calcitriol concentration assessment will be taken 1, 2 and 4 hours after IMP administration

- The subject will be issued with an Injection Site Reaction Diary and instructed to view their injection site (s) at the same time each day and record their findings every day for 3 days.(See Section 7.4.5)

7.3.3 On-study clinic visits

7.3.3.1 Visit 3 (Day 8)

The subject will return to the clinic 7 days after administration of the IMP for visit 3. The following procedures will be performed:

- Symptom directed physical examination (See Section 7.4.1)
- Vital Signs (See Section 7.4.1)
- DAS28CRPv4 Evaluation (See Section 7.4.7)
- Review of Injection Site Reaction Diary (See Section 7.4.5)
- Blood samples for:
 - Haematology including ESR (See Section 7.4.3.)
 - Clinical chemistry including CRP (See Section 7.4.3)
- Blood Samples for Immunological Assessment including (see Sections 7.4.3 and 7.4.4):
 - Tetramer analysis
 - Exploratory Immune assays;
- Blood Samples for Pharmacokinetic (Calcitriol) assessment (Part B only, See Section 7.4.3)
- Urine samples for urinalysis (See Section 7.4.3)
- Adverse event and concurrent medication questioning (see sections 9 and 10)
- Urine sample for pregnancy testing (See Section 7.4.6, part B only)

For subjects undergoing Part B of the study, once the above assessments have been performed the IMP will be administered:

- Subjects will be observed and vital signs will be measured at 15 and 30 minutes following the administration of IMP
- Subjects will remain in the clinic for at least four hours post-administration of IMP
- Blood samples for calcitriol concentration assessment will be taken 1, 2 and 4 hours after IMP administration
- The subject will be issued with an Injection Site Reaction Diary and instructed to view their injection site (s) at the same time each day and record their findings every day for 3 days (See Section 7.4.5).

7.3.3.2 Visit 4 (Day 15)

The subject will return to the clinic fourteen days following the first administration of the IMP for visit 4. The following procedures will be performed:

- Symptom directed physical examination (See Section 7.4.1)

- Vital Signs (See Section 7.4.1)
- DAS28CRPv4 Evaluation (see Section 7.4.7)
- For Subjects in Part B, review of Injection Site Reaction Diary (See Section 7.4.5)
- Blood samples for:
 - Haematology including ESR (See Section 7.4.3.)
 - Clinical chemistry including CRP (See Section 7.4.3)
- Blood Samples for Pharmacokinetic (Calcitriol) assessment (Part B only, See Section 7.4.3)
- Urine samples for urinalysis (See Section 7.4.3)
- Adverse event and concurrent medication questioning (see Sections 9 and 10)
- Urine sample for pregnancy testing (Part B only)

For subjects undergoing Part B of the study, once the above assessments have been performed the IMP will be administered:

- Subjects will be observed and vital signs will be measured at 15 and 30 minutes following the administration of IMP
- Subjects will remain in the clinic for at least four hours post-administration of IMP
- Blood samples for calcitriol concentration assessment will be taken 1, 2 and 4 hours after IMP administration
- The subject will be issued with an Injection Site Reaction Diary and instructed to view their injection site (s) at the same time each day and record their findings every day for 3 days (See Section 7.4.5).

7.3.3.3 Visit 5 (Day 29)

The subject will return to the clinic 21 days following the first administration of the IMP for visit 5. The following procedures will be performed:

- Symptom directed physical examination (See Section 7.4.1)
- Vital Signs (See Section 7.4.1)
- DAS28CRPv4 Evaluation (see Section 7.4.7)
- For Subjects in Part B, review of Injection Site Reaction Diary (See Section 7.4.5)
- Blood samples for:
 - Haematology including ESR (See Section 7.4.3.)
 - Clinical chemistry including CRP (See Section 7.4.3)
- Blood Samples for Immunological Assessment including (See Sections 7.4.3 and 7.4.4):
 - Tetramer analysis
 - Anti-CCP2 titre (See Section 7.4.3)
 - Exploratory immune assays
- Urine samples for urinalysis (See Section 7.4.3)
- Adverse event and concurrent medication questioning (see sections 9 and 10)

